Cover Page

Behavioral Effects of Drugs (Inpatient): 38

NCT03954938

February 20, 2019

BACKGROUND

Cocaine use disorder is an unrelenting public health concern. Nearly 1 million people met criteria for cocaine use disorder in 2017, a rate that has remained stable for the past decade. Cognitive behavioral therapy (CBT) is a psychosocial treatment that durably reduces cocaine use. However, CBT does not promote cocaine abstinence or eliminate cocaine relapse in all patients. It is also not implemented in many treatment clinics because it requires substantial clinical time commitment. Moreover, the mechanisms underlying the efficacy of CBT are not well understood. Determining the mechanisms that drive the efficacy of CBT will promote refinement and enhancement of CBT methods, and ultimately its implementation, thereby maximizing the impact of CBT on the public health burden posed by cocaine use disorder.

Two primary, interrelated components of CBT are the decisional analysis of positive and negative outcomes resulting from cocaine use and the regulation of cocaine craving. These components target the diminished control over cocaine use despite negative consequences, exacerbated by craving, that characterizes cocaine use disorder. It is believed that the emphasis on the negative consequences of cocaine use and reductions in craving promoted by CBT directly reduces cocaine taking, but this hypothesis has not been tested.

Human laboratory research provides a means of determining the mechanisms underlying effective treatments for drug use disorders. Research with alcohol, cigarettes and methamphetamine has modeled the decisional analysis and craving regulation aspects of CBT by instructing subjects to focus on the positive or negative aspects of drug use when presented with drug cues. Consideration of negative or long-term aspects of substance use reduced craving for those substances. *Preliminary data from our laboratory has extended those findings to show that focusing on the negative aspects of cocaine use reduces cocaine craving.* Whether reduced craving drives reductions in cocaine self-administration remains to be determined.

We have developed human laboratory cocaine self-administration procedures that have strong predictive validity for determining the impact of behavioral manipulations on cocaine taking. For example, we have shown that the availability of mutually exclusive alternative reinforcers reduces cocaine self-administration. This arrangement models another effective psychosocial intervention, contingency management. In this pilot study, our self-administration procedures will be adapted to evaluate the influence of decisional analysis/craving regulation features of CBT on cocaine self-administration, thereby determining how these components contribute to the ability of CBT to promote biologically verified cocaine abstinence.

The specific aim of this project is to demonstrate that the decisional analysis/craving regulation aspects of CBT reduce cocaine self-administration in subjects with cocaine use disorder through diminished craving responses. Thirty non-treatment seeking human subjects meeting diagnostic criteria for cocaine use disorder will complete an outpatient, crossover, placebo-controlled study consisting of 1 practice and 9 experimental sessions. In each experimental session, the reinforcing effects of intranasal cocaine (0, 40 or 80 mg) will be determined under one of three regulation of craving conditions that simulate CBT decisional analysis (i.e., negative instruction, positive instruction or a neutral “look” condition). After sampling the dose of cocaine available in each session, subjects will complete the craving manipulation assigned to that session, they will then rate their craving and finally they will have the opportunity to earn the sampled dose in a progressive-ratio procedure. We hypothesize that focusing on the negative effects of cocaine use will decrease craving and reduce cocaine self-administration relative to the positive and “look” conditions, and that craving will be positively correlated with self-administration outcomes.

2. OBJECTIVES

The primary objective of this study is to determine the influence of a craving manipulation on the reinforcing effects of cocaine.

3. STUDY DESIGN

A double-blind, placebo-controlled, crossover design will be used in this experiment. A completely within-subject design will be used such that each subject will receive all possible dose conditions.

4. STUDY POPULATION

Up to 100 individuals will be screened to participate in this study. We intend to enroll thirty (15 male and 15 female) completers into the study. These individuals must be English-speaking, English-reading subjects 18-55 years of age of varying ethnic backgrounds. Enrollment in this study will occur between January 15, 2019 and January 14, 2020. Subjects will be required to provide legal proof of age. Subjects must be healthy and without contraindications to cocaine. Subjects must also report recent use of cocaine and must meet diagnostic criteria for cocaine use disorder using the Structured Clinical Interview for DSM-5 (SCID). Subjects must provide a cocaine positive urine during screening to verify cocaine use status. Screening procedures for all subjects will include a medical history questionnaire, laboratory chemistries (blood chemistry screen, complete blood count, ECG, and urinalysis), and a brief psychiatric examination. These procedures will be conducted under our lab's screening protocol (44379). Chemistry values and screening outcomes must be deemed normal. If chemistry values or screening outcomes fall outside normal ranges, a study physician must deem them clinically insignificant for a subject to be enrolled. An electrocardiogram must also be within normal limits. Any potential subject with a history of serious physical disease, current physical disease, impaired cardiovascular functioning, chronic obstructive pulmonary disease, history of seizure, or current or past histories of serious psychiatric disorder that in the opinion of the study physician would interfere with study participation will be excluded from participation. Subjects with current or past histories of substance use disorder that are deemed by the doctor to interfere with study completion will also be excluded from participation. Female subjects must be using an effective form of birth control (e.g., birth control pills, surgical sterilization, IUD, cervical cap with a spermicide, condoms, or abstinence) in order to participate. A urine pregnancy test will be conducted before the start of each experimental session to ensure that female subjects do not continue in the study if pregnant. All study subjects will be judged by the study physician, [name] or [name] to be healthy.

During the initial screening process, potential subjects will be asked to provide a urine specimen that will be screened for the presence of recent use of amphetamine, benzodiazepines, barbiturates, cocaine, tetrahydrocannabinol (THC), and opioids. In order to participate in an experimental session, subjects must provide a urine negative for recent use of amphetamine, barbiturates, benzodiazepines, and opioids on each day of their participation. Subjects will be allowed to continue if they test positive for recent use of cocaine or marijuana (THC) if they pass the sobriety test and have vital signs within acceptable limits (see below).

5. SUBJECT RECRUITMENT METHODS AND PRIVACY

Subjects are recruited primarily through formal advertisement (i.e., regular newspaper advertisements placed generally in free newspapers), local flyers posted in public areas (e.g., bars, restaurants, stores), and by word-of-mouth. These advertisements are approved under our screening protocol (IRB # 44379). Subjects will make initial contact by phone with one of our recruiters who have completed the research training and HIPAA compliance web-based teaching models. If the subject self-discloses information that would make him/her potentially eligible for the study, they will be invited to come in for a screening appointment. Screening is completed by one of our research assistants at the UK Laboratory of Human Behavioral Pharmacology (LHBP) and is covered under our approved screening protocol (IRB # 44379). Study investigators may interact with subjects in this setting and appropriate cautions are in place to ensure privacy during the intake process.

6. INFORMED CONSENT PROCESS

All potential subjects that are identified using the subject recruitment methods noted above will provide informed consent prior to participating in the protocol. Subjects that meet the eligibility criteria noted above will come to the LHBP, undergo a field sobriety test, and provide an expired air sample that will be tested for the presence of alcohol. If the subject passes the field sobriety test (walk and turn, one-leg balance [timed], finger-to-nose and backwards-counting tasks), and the expired air sample is negative, he or she will then be given a copy of the approved informed consent document to read and sign. After reading the consent document, the PI or one of the Co-Is on this protocol will address any questions the subject may have in order to assess the subject's

understanding of the protocol. After this, the subject will receive a copy of the informed consent document and will sign a form indicating that they have received a copy of the form they read and signed.

7. RESEARCH PROCEDURES

General Procedures. Subjects that meet the inclusion criteria will participate as outpatients at the University of Kentucky LHBP and Clinical Services Core (CSC). Subjects will be discharged at the end of each day, provided that they meet release criteria.

This experiment will require each subject to complete a total of one practice and nine experimental sessions over approximately two to three weeks. Experimental sessions will be conducted as outlined in the table below. We would like to note that the order of the experimental sessions (i.e., dose tested and craving manipulations) will be randomized across subjects. The practice session will familiarize subjects with the experimental routine and tasks, but no drug will be administered and subjects will receive instructions on each of the craving manipulation conditions (positive, negative, and look [neutral]).

Time	
0800	Arrival at LHBP. Drug and alcohol use restriction compliance verified. Transport to CSC.
0900	Baseline craving, subjective-effect and physiological measures completed.
1000	Subject samples intranasal dose available for that session. Subjective-effect and physiological measures completed at 15-minute intervals for 45 minutes. Commodity purchase tasks completed 15 minutes after sampling dose.
1045	Subject completes regulation of craving manipulation assigned for that session (positive, negative or look) and rates craving.
1050	Subject offered opportunity to work for dose on progressive-ratio schedule.
1100	Dose administered, if earned and physiological measures are within acceptable limits.
1115	Subjective-effects and physiological measures completed.
1130	Craving manipulation, craving measurement, progressive-ratio procedure and subjective-effects and physiological measures sequence completed. Repeats 4 more times at 45-minute intervals.
1530	Discharge from CSC. Return to LHBP for final sobriety testing, payment and release.
Note	Cocaine dose and craving manipulation will be presented in random order. A fully factorial design will be used so that all possible combinations are tested once each over nine sessions.

Subjects will be encouraged to abstain from illicit drugs for the duration of the study and from alcohol for the 12 hours prior to, and following, each experimental session. They must also agree to abstain from solid food and caffeine for 4 hours before each experimental session. Subjects will arrive at the LHBP at approximately 0800 hours. Upon arrival at the LHBP, a breathalyzer and a field sobriety test will be conducted, a urine sample collected, and pre-session paperwork completed. A breathalyzer positive for alcohol or a urine sample positive for recent use of amphetamines, benzodiazepines, barbiturates, or opioids will preclude the subject from participation in the session. If a subject tests positive for recent use of cocaine or marijuana (THC), [name] or [name] must be notified. Subjects will only be allowed to participate in a session with a marijuana or cocaine positive urine if they pass the sobriety testing and baseline cardiovascular measures are within acceptable limits (i.e., heart rate < 90 bpm, if systolic pressure < 140, or diastolic pressure < 90). Moreover, intranasal cocaine doses may not be administered until two hours following all subjects' arrival, regardless of the outcome of their urinalysis. Subjects will then be provided with a standard, fat- and caffeine-free breakfast. Prior to beginning each experimental session, subjects that report smoking tobacco cigarettes will be allowed to smoke one cigarette.

At 0830, subjects will be transported to the CSC. Physiological measures will be recorded at 15-minute intervals upon arrival at the CSC. At 1000, subjects will sample the dose of intranasal cocaine available that day (0, 40 or 80 mg). After sampling the drug, subjects will complete the subject-rated measures. Subjects will then make 5 choices to self-administer the sampling dose after completing the craving manipulation. Choices will be separated by 45 minutes. Drug administration will be withheld if heart rate > 90 bpm, if systolic pressure > 140 or

diastolic pressure > 90. Subjects will be excluded from further research participation if at any time during an experimental session heart rate increases above 130 bpm, diastolic pressure increases above 110 mmHg or systolic pressure above 180 mmHg.

At approximately 1530, subjects will be transported back to the LHBP and provided lunch. Subjects will then complete post session sobriety testing. If no drug effects are detected and vital signs are within acceptable limits (i.e., heart rate < 100 bpm, if systolic pressure < 150, or diastolic pressure < 100), subjects will be released from the laboratory at approximately 1630 h. At this time, payment for that day's session will be given to the subject. If drug effects are evident at the end of the experimental session, subjects will remain at the laboratory until these effects dissipate. Subjects must agree not to operate a motor vehicle or heavy machinery for 6 hours after leaving the laboratory.

Apparatus. Behavioral testing will be conducted at the LHBP and CSC. Subjects will be tested using an individual laptop computer that automates behavioral tasks.

Regulation of Craving Manipulation. This task was developed based on previous work with cigarettes, methamphetamine and alcohol (Kober et al., 2010a; 2010b; Lopez et al., 2015; Naqvi et al., 2015) and will be essentially identical to what was used in our pilot study (Strickland et al., 2016). At the outset of the practice session, participants will be presented with cocaine images and trained on each of the three strategies (positive, negative, look [neutral]), based on previous work with methamphetamine users (Lopez et al., 2015). During positive trials, participants will be told to focus on positive subjective effects of consuming cocaine (e.g., stimulation, good effects). During negative trials, participants will be told to focus on negative subjective effects of consuming cocaine (e.g., feeling sad the next day, guilt over money spent or damage to personal relationships). During look trials, participants will be told to respond naturally to the cocaine stimulus.

During the actual manipulation in experimental sessions, subjects will be presented 30 trials depicting cocaine images. Each trial will begin with an instruction presentation (i.e., positive, negative, look) followed by 6-second image presentation. The instruction presentation will remain constant within each experimental session. Images will be presented in random order from a bank of 300 images to minimize habituation. After each image offset, subjects will rate craving for cocaine using a 0-10 visual analog scale (0 = Not at All; 10 = Very Much) (Lopez et al., 2015). Craving, averaged across all trials in a session, will be the primary outcome. The manipulation will be repeated prior to each self-administration opportunity.

Progressive-Ratio Procedure. Following a 30-image trial, subjects will be offered the opportunity to earn the sampled cocaine dose on the Progressive-Ratio Procedure. We have a long history of using this procedure to assess the reinforcing effects of stimulant drugs ([name], 2008), including cocaine ([name] et al., 2010a; 2012a). It yields orderly, dose-related self-administration outcomes. Subjects will have a total of five opportunities to earn the dose they sampled at the outset of the session in order to provide multiple replication trials to determine the impact of the craving manipulation on drug self-administration (Ferster and Skinner, 1957; Spiga and Roache, 1997). The initial response requirement for a dose will be 400 mouse clicks. Response requirements will increase by 200 for each subsequent dose. For example, if a subject chooses cocaine at the first trial, earning that dose would require 400 responses. At the second opportunity, if he/she chooses to earn cocaine again, earning that dose would require 600 responses. If he or she elects not to earn cocaine at any given opportunity, the response requirement would not increase for the next opportunity. If a subject were to choose cocaine across all opportunities, the response requirements would be 400, 600, 800, 1000 and 1200 responses. The primary outcome is the number of cocaine doses earned.

Subjective-Effects and Physiological Measures. A subjective-effects questionnaire and physiological measures will also be used to assess cocaine effects and monitor safety.

Subjective-Effects Measures. One subject-rated questionnaire that measure various aspects of mood and drug effect will be used: the Drug-Effect Questionnaire. This questionnaire is sensitive to stimulant drug effects ([name] et al., 2003).

Physiological Measures. Heart rate, blood pressure, heart rhythmicity and oral temperature will be recorded using a digital monitor. These outcomes are sensitive to stimulant drug effects ([name] et al., 2008; 2016).

Commodity Purchase Task (Appendix B). Commodity purchase tasks will be used to assess economic demand for chocolate, cigarettes, alcohol, and the cocaine sampling dose (Amlung et al., 2015; Bruner and Johnson, 2014; Murphy and MacKillop, 2006; [name] et al., ongoing). In these tasks, subjects are asked to indicate the hypothetical number of commodity units (i.e., 12 oz. sodas) they would purchase at a future date at monetary increments ranging from \$0.00 (free) to \$140/unit. In the cocaine task, participants will be asked to make choices based on the sampling dose they received earlier in the session. All choices are hypothetical and will not be purchased or administered. Subjects will complete the Commodity Purchase Tasks following approximately .25 h after the sampling dose.

Drug Dose and Administration. All drugs will be administered under double-blind conditions and under medical supervision. Doses of cocaine HCl will be prepared by weighing out the appropriate amount of powdered cocaine. The powder will then be mixed with lactose monohydrate powder, N.F. to make a total of 80 mg powder. Placebo will be prepared in an identical fashion, but will contain only lactose monohydrate powder. Doses of cocaine will be prepared individually for each subject. Doses of 0, 40 and 80 mg intranasal cocaine will be placed into individual glass vials labeled for each subject for each sampling session. The unit doses of cocaine proposed for the study have been administered to human subjects under similar controlled medical and laboratory conditions without adverse incident by the study team ([name] et al., 2008; 2010; 2016).

Data Analysis. All data will be analyzed using SPSS (IBM Corporation, Armonk, NY). To test our primary hypothesis, self-reported craving scores and number of cocaine doses earned will be analyzed using two-factor repeated-measures General Linear Model (GLM) with data from the 30 subjects who complete the protocol. The α level will be set at $p \leq 0.05$. Data from subjects who do not complete will not be included in the analyses. Cocaine Dose (0, 40 and 80 mg) and Craving Manipulation (positive, negative and look) will be the factors of the ANOVA. A significant change in craving or self-administration will be inferred if the Interaction of Cocaine Dose and Craving Manipulation attains statistical significance. If the interaction attains statistical significance, the mean square error term will be used to conduct Tukey's HSD post-hoc test to make appropriate pair-wise comparisons. If baseline measures (e.g., craving) differ across conditions, they will be entered into the analysis as covariates. To test our secondary hypothesis, craving scores will be averaged for each of the nine conditions and compared with self-administration outcomes using Pearson correlations. Subjective-effect and physiological data following the sampling dose will be averaged across craving manipulation conditions because they will be collected prior to the craving manipulation and analyzed using cocaine dose and time as factors in a repeated-measures GLM. Exploratory analyses considering relevant biological variables (i.e., sex, age and race/ethnicity) will also be conducted.

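### The nine-session crossover is analysed without a session term, so any drift common to subjects, if present, stays in the error and costs precision, though not validity

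*Combined protocol and SAP*

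**What the plan says.** Section 3 sets a crossover: "A completely within-subject design will be used such that each subject will receive all possible dose conditions". Section 7 (General Procedures) asks for "a total of one practice and nine experimental sessions over approximately two to three weeks" and states that "the order of the experimental sessions (i.e., dose tested and craving manipulations) will be randomized across subjects". The note to the timetable adds: "A fully factorial design will be used so that all possible combinations are tested once each over nine sessions". No Latin square, blocking or other balancing of session position is described.

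The Data Analysis paragraph of Section 7 gives the only model for the two primary outcomes, craving and doses earned. It is a "two-factor repeated-measures General Linear Model (GLM) with data from the 30 subjects who complete the protocol", in which "Cocaine Dose (0, 40 and 80 mg) and Craving Manipulation (positive, negative and look) will be the factors of the ANOVA". The decision rests on the interaction, with Tukey comparisons on the same mean square error if it is significant. No session, period or sequence term appears anywhere.

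Three provisions bear on drift:

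- A drug-free practice session (General Procedures).
- The image bank (Regulation of Craving Manipulation): "Images will be presented in random order from a bank of 300 images to minimize habituation".
- A rule that baseline measures such as craving become covariates if they differ across conditions (Data Analysis).

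**The concern.** In a crossover with nine periods, the session in which each condition was observed is always known, and adjusting for it is the usual precaution. Two features make drift plausible here. The image bank cannot prevent repetition at the planned exposure, and the progressive-ratio task, at 400 to 1,200 clicks per dose, recurs in every session.

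Each of the nine cells is seen once per subject. A session-to-session change therefore falls unevenly on the conditions within a subject and is recorded as unexplained within-subject variation. At stake is the sensitivity of a 30-subject study whose conclusion depends on a 4-df interaction. The documents give no power calculation, so there is no stated margin to absorb a loss.

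**Working it through.** There is no figure in the documents to reproduce, because no SD, effect size or power is given. The drift is therefore an assumption and is shown over a range.

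**Inputs from Section 7.** 30 completers; 9 sessions; 3 × 3 cells, each once per subject in random order; 30 image trials per manipulation; 5 manipulations per session, one before each opportunity; 300 images.

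**Image exposure.** 30 × 5 × 9 = 1,350 presentations per subject, and 1,350 / 300 = 4.5 views per image on average. If the timetable is read as six manipulations per session, the figures are 1,620 and 5.4. Images repeat on either reading.

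**Variance inflation.** For a random order of sessions 1 to 9, the sample variance of session position (divisor 8) is 60 / 8 = 7.5. A contrast with weights c that sum to zero has per-subject position variance 7.5 × Σc². Its residual variance is σ² × Σc². With drift b in units of σ per session, the ratio of total to residual variance is 1 + 7.5b² for every contrast.

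| b (residual SDs per session) | Change from session 1 to 9 (8b) | Extra variance |
|---|---|---|
| 0.05 | 0.4 SD | 1.9% |
| 0.1 | 0.8 SD | 7.5% |
| 0.125 | 1 SD | 11.7% |
| 0.2 | 1.6 SD | 30% |
| 0.25 | 2 SD | 46.9% |

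**The same effect seen as chance imbalance of order, 30 subjects.**

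- Two single cells: Σc² = 2, so the SD of the difference in mean position is √(7.5 × 2 / 30) = 0.71 session.
- Two manipulation conditions over all doses: Σc² = 6 × (1/3)² = 2/3, so the SD is √(7.5 × (2/3) / 30) = 0.41 session.
- At b = 0.2, the 95% ranges are 1.96 × 0.2 × 0.71 = ±0.28 SD for two cells and 1.96 × 0.2 × 0.41 = ±0.16 SD for negative versus look.

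For two cells, the variance of this shift is 15b² / 30 = 0.5b². Divided by the no-drift variance 2 / 30, that is 7.5b², the inflation above.

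**Interaction test.** Simulation used 3,000 runs per scenario, independent random orders and equal-covariance errors. The true interaction was set to give 80% power without drift (an assumption). The planned analysis was compared with a subject + condition + session model (session as a factor).

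| Change from session 1 to 9 | Power, planned | Power, with session | Type I error, planned | Type I error, with session |
|---|---|---|---|---|
| 0 | 80.1% | 79.5% | 5.2% | 5.3% |
| 1 SD | 74.4% | 78.8% | 4.8% | 4.9% |
| 2 SD | 60.5% | 80.0% | 5.4% | 5.1% |

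**Form of the replacement model.** A mixed model with only subject random pools all within-subject error, whereas the planned ANOVA tests the interaction against its own stratum (4 and 116 df). With assumed subject-by-dose and subject-by-manipulation SDs of 0.7 and residual SD 1, simulation under the null gave these rejection rates:

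- Pooled model: about 0.3% for the interaction and 12 to 13% for the manipulation main effect.
- Planned ANOVA: about 5% for both.
- Interaction stratum kept and linear session added: 5.0%.

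**The case against.** The strongest reply is that nothing here is invalid. Random order protects the comparison on average, and the simulated type I error of the planned test stays near 5%. A reader might infer from the missing term that the primary result would be biased or its error rate inflated; the design does not support that.

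The harm is also conditional. The documents do not show that drift exists. At b = 0.05 the loss is about 2%. A drift of 0.2 dose per session, if the residual SD were 1 dose, would mean a change of 0.2 × 8 = 1.6 doses from first to last session on an outcome limited to 0 to 5. A fixed session term removes only drift shared by all subjects and of the same size in every cell, so the gains shown are best cases.

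The plan has safeguards. The practice session should take up early learning. The image bank reduces repetition. Baseline craving, measured each session, could absorb some drift if that covariate is used. These points stand, and it would be too strong to say that all drift must remain in the error. None of the safeguards replaces the term, however. Practice comes before session 1, the bank still repeats images, and the covariate enters only when baselines differ across conditions.

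A reader might also count the inflated variance and the chance order imbalance as two separate harms. They are one quantity and should not be added. Nor does the 0.71-session figure apply to negative versus look over doses, where the SD is 0.41. Finally, the protocol calls this a pilot study, which lowers the stakes.

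**Conclusion.** The point holds as a question of precision. The planned model leaves out a known source of variation in a nine-period crossover. If drift common to subjects is present, contrast variance rises by a factor of 1 + 7.5b². The loss is trivial for a total drift of 0.5 SD or less (2.9% at 0.5 SD). It becomes material from about 1 SD, where interaction power falls from 80% to about 74 or 75%.

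These figures assume linear, additive drift, errors with equal covariance, and an interaction sized for 80% power. The first and third cannot be checked against the documents, and no drift size can be taken from them. The argument for acting is one of balance: with no drift, the term cost 0.6 of a percentage point of simulated power (80.1% versus 79.5%). This is a worthwhile low-cost improvement, not a defect that threatens the trial's conclusions.

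**What to change.** Before unblinding, pre-specify one model for craving and for doses earned:

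- Fixed effects: dose, manipulation, their interaction, and session number (1 to 9). State in advance whether session is linear or categorical.
- Random effects: subject, subject-by-dose and subject-by-manipulation, so that each effect is tested against the same error stratum as in the planned ANOVA. An unstructured within-subject covariance is an alternative, but with nine cells it has 9 × 10 / 2 = 45 parameters to estimate from 30 subjects, so the random-effects form is easier to support.
- Post-hoc comparisons: take them from the session-adjusted means and the error of this model.

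Do not replace the planned ANOVA with a model that has subject as the only random effect; that changes the error structure and can distort both tests.

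The cost is 1 or 8 df, which leaves 115 or 108 of the 116 in the interaction stratum if the whole cost falls there, and somewhat more analysis work. No new data are needed. If enrolment has not started, balancing session position by design would reduce the chance imbalance as well, but the analysis change does not depend on it.

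### The release limits, and the parallel entry limits for cocaine- or THC-positive subjects, join three vital-sign cut-offs with *or*, so read literally one in-range value is enough

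*Combined protocol and SAP*

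**What the plan says.** All the relevant rules are in Section 7, Research Procedures, of the combined protocol and SAP.

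- **Release.** The condition has two parts: "If no drug effects are detected and vital signs are within acceptable limits". An *i.e.* parenthesis then defines the limits as "heart rate < 100 bpm, if systolic pressure < 150, or diastolic pressure < 100".
- **Hold.** The next relevant instruction concerns drug effects and gives no number: "If drug effects are evident at the end of the experimental session, subjects will remain at the laboratory until these effects dissipate".
- **Entry with cocaine- or THC-positive urine.** The subject must pass sobriety testing, and the plan also requires that "baseline cardiovascular measures are within acceptable limits". The limits are again given in an *i.e.* parenthesis: "heart rate < 90 bpm, if systolic pressure < 140, or diastolic pressure < 90". Section 4 sends the reader forward to these limits.
- **Withholding a dose.** "Drug administration will be withheld if heart rate > 90 bpm, if systolic pressure > 140", or if diastolic pressure exceeds 90. The session table adds its own dosing condition: "Dose administered, if earned and physiological measures are within acceptable limits".
- **Exclusion from further participation.** This applies if at any time in a session "heart rate increases above 130 bpm, diastolic pressure increases above 110 mmHg or systolic pressure above 180 mmHg".

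**The concern.** A stop rule and a go rule need opposite connectives. To stop when any value is too high, the breaches are joined by *or*. To proceed only when every value is acceptable, the limits are joined by *and*. The release and entry rules are go rules, yet they carry the connective of a stop rule. Each parenthesis is introduced by *i.e.*, so it defines the acceptable range and does not merely illustrate it.

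What is at stake is subject safety at discharge. These are outpatients who may receive one sampling dose and up to five earned doses of as much as 80 mg each, and who leave at about 1630 the same day. Section 9 names raised heart rate and blood pressure as common effects of cocaine, so these limits guard against something the protocol expects. As written, staff could release a subject with two of three vital signs over the limits and still comply with the numeric rule. A monitor checking against the text would have no deviation to record.

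**Working it through.** The plan gives no calculated figure to reproduce. The check is logical, with simple arithmetic on the stated limits.

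**Inputs (Section 7, General Procedures)**

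| Rule | Heart rate (bpm) | Systolic (mmHg) | Diastolic (mmHg) | Connective | Correct for its purpose? |
|---|---|---|---|---|---|
| Withhold dose | > 90 | > 140 | > 90 | or | Yes: any breach stops dosing |
| Exclude from further participation | > 130 | > 180 | > 110 | or | Yes: any breach excludes |
| Entry (cocaine- or THC-positive) | < 90 | < 140 | < 90 | or | No |
| Release | < 100 | < 150 | < 100 | or | No |

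**Step 1: count the patterns.** Three vital signs, each in or out of range, give 2 × 2 × 2 = 8 patterns.

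| Values in range | Patterns | Passes with *or* | Passes with *and* |
|---|---|---|---|
| 3 | 1 | 1 | 1 |
| 2 | 3 | 3 | 0 |
| 1 | 3 | 3 | 0 |
| 0 | 1 | 0 | 0 |
| Total | 8 | 7 | 1 |

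These are counts of logical patterns, not probabilities.

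**Step 2: release example, heart rate 95, systolic 175, diastolic 105.**
- Rule with *or*: 95 < 100, so the vital-sign part is met.
- Rule with *and*: not met. Systolic is 175 − 150 = 25 mmHg over and diastolic is 105 − 100 = 5 mmHg over.
- Exclusion rule: not triggered, since 95 ≤ 130, 175 ≤ 180 and 105 ≤ 110.

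**Step 3: entry example, heart rate 85, systolic 165, diastolic 105.**
- Rule with *or*: 85 < 90, so the cardiovascular part is met.
- Rule with *and*: not met. Systolic is 165 − 140 = 25 mmHg over and diastolic is 105 − 90 = 15 mmHg over.
- Withholding rule: triggered, since 165 > 140 and 105 > 90. The subject enters the session but is not dosed at those values.

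**Step 4: look for other text that would block the release example.**
- The hold instruction is tied to evident drug effects and sets no vital-sign limit.
- The withholding rule, the session-table condition and the statement in Section 17 that drug is not given when heart rate or blood pressure is out of range all govern dosing, not release.
- The exclusion rule governs further participation. It sets no release limit, and the example does not reach it anyway.
- Section 10 says staff know the acceptable parameters and that these are posted in the session rooms. It does not say what is posted for release, or that all three values must be met.

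None of these supplies a numeric release limit or says that all three values must be in range.

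**Likely origin (inference).** The entry and release limits share the stray *if* of the withholding rule. They look like that rule with the inequality signs reversed and the connective left unchanged.

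**The case against.** The strongest reply is that nobody would apply the rule this way. The governing words are plural and speak of vital signs, or cardiovascular measures, being within limits. A subject at 175/105 plainly does not meet that description, and the parenthesis is too garbled to pass as a deliberate set of alternatives. This is good evidence of intent, and it settles which correction is right. It does not make the rule correct, because the parenthesis is what defines the limits.

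Second, release also requires that no drug effects are detected. Section 7 describes physiological measures as a way to assess cocaine effects, and heart rate and blood pressure as sensitive to stimulants. Raised pressure could therefore be treated as a detected drug effect and trigger the hold. That softens the problem, but it leaves the decision to judgement without a number, and the release sentence lists drug effects and vital signs as separate conditions.

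Third, the release example is constructed. If the five dosing opportunities run at 45-minute intervals from the 1100 dose, the last falls at about 1100 + 4 × 45 minutes = 1400, some two and a half hours before release, and that dose could be given only with all values in range. This is fair, and it is why no frequency is claimed.

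Fourth, the entry wording has little practical consequence because dosing remains blocked. This stands: at entry the fault is mainly an inconsistency with the withholding rule, and the weight of the point is on release.

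**Conclusion.** The concern holds: both sets of limits are wrong as written. Read literally, the vital-sign part of the release rule allows discharge with two of three values over the protocol's own limits, as in the example that is 25 mmHg over on systolic and 5 mmHg over on diastolic pressure. The only remaining check is the sobriety and drug-effect assessment. The entry rule has the same fault, but the withholding rule protects dosing there.

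The conclusion rests on a literal reading of the text. Staff may well apply all three limits in practice, and the documents give no data on how often the two readings would differ. The release rule does not conflict with the withholding rule; it is a separate error. The effect is on subject safety only. Nothing here bears on sample size, the significance level or the analysis. The correction should be made, though it is not a flaw in the trial's design.

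**What to change.** In Section 7, General Procedures, delete the stray *if* and replace *or* with *and* in two places:

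- **Entry with cocaine- or THC-positive urine:** all of heart rate < 90 bpm, systolic < 140 mmHg and diastolic < 90 mmHg.
- **Release:** all of heart rate < 100 bpm, systolic < 150 mmHg and diastolic < 100 mmHg.

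Leave *or* in the withholding and exclusion rules, where it is correct. The responsible medical investigator should confirm the wording, and the limits posted in the session rooms (Section 10) should be checked against it.

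The cost is two one-line wording amendments and a check of the posted limits. The numeric limits, schedule, sample size and analysis do not change.
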